tests, partly for serum concentration determination. They are also informed that they will receive at least 1 year of follow-up in RVD, against the usual ½ year. At the visit after 1 year, the same clinical tests and scales are carried out as during the patients' preliminary examination, and matters relating to compliance are queried. The other group (intervention group) will have an extra blood sample taken if they experience side effects from the treatment within the first 2 months. Everyone also has one extra blood test at each The ½- and 1-year check-ups. In addition, they will also be followed for at least 1 year against the normal ½ year. At the 1-year check-up, the same clinical tests and scales are carried out as in the pre-examination, and matters relating to compliance are queried. Subsequently, the respective compliance, distribution of serum concentrations, as well as the importance of serum concentration determination and derived dose regulation for the overall clinical response after 1 year (assessed on MMSE, ACE, NPI, DAD and CGI). A comparison is made of the occurrence, duration and outcome of side effects in the 2 groups, including the proportion of patients who had to change preparations or abandon medical treatment due to side effects. The project manager (alternatively the person performing the test) is blinded in relation to which group the patient is randomized to and to the result of serum values. The final statistical analysis of the clinical value of serum determinations and derivative monitoring is performed by an independent statistician. No participants will receive any form of remuneration for participation in the project. Any additional costs for transport are covered according to the appendix. Use of journal information Journal information is used to identify the target group, including clarifying inclusion and exclusion criteria (see these). During the project period of one year, the journal is used to document and monitor any side effects or unintended events, just as all possible side effects or unwanted events are entered into the patient's CRF.

FLOWCHART FOR PROJECT "MONANTI"

Inclusion criteria for participants

- All patients [evaluated at RVD] who after diagnostic assessment has been completed, meet the criteria for
- Alzheimer's Dementia (AD), (NIA-AA, (1)), Dementia with Lewy-Bodies (DLB) (15) or Parkinson's Disease Dementia (PDD) (18), and
- who are scheduled for treated with Donepezil or Memantine and

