- At the weekly interdisciplinary diagnostic conference at RVD, all eligible patients are noted. An anonymized list is kept, which ensures that all patients who meet the criteria for participation are offered participation. An anonymized list of both included and non-included patients is maintained continuously [screening list].
- Inclusion criteria are assessed.
- Exclusion criteria are assessed.
- If the patient meets the criteria, participation in the project is offered at the information visit [the visit during which the diagnosis is presented to the patient]. Written information is provided and time to reflect on the offer of study participation is provided.
- Possible participants are contacted by telephone within one week, and those who wish to participate are immediately invited to an enrollment visit.

- Patient and accompanying relatives are informed both orally and in writing about the study's purpose, background, execution and any side effects/possible harms of participation.
- The patient is again offered time to reflect.
- If the patient wishes to participate, a declaration of consent [must be] signed [by the patient].
- Randomization is carried out to control or intervention group. The participant and the relative are informed via the project nurse about which group they have been allocated to.
- The participant is registered in the Case Report Form (CRF).
- The project nurse registers the participant's trial number [randomization number], which will be the only identification for the subsequent examinations (for reasons of blinding).
- A blood sample for genetic analysis is taken from all participants.
- Participants in the intervention group are offered an extra blood test if side effects develop within 2 weeks to 2 months after starting treatment. The dose is adjusted in relation to the serum concentration, if necessary the dosage and/or drug prescribed is changed. At the ½-year follow-up, one extra blood test is collected for all participants. The dosage is adjusted according to the serum concentration, if deemed appropriate an alternative [anti-dementia] drug is prescribed.
- Participants belonging to the control group will not undergo any extra procedures, apart from a single blood test at the end of the project.

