As by custom in ordinary clinical practice [in RVD], all patients and relatives are informed about potential side effects at the start of treatment and dose adjustments. Side effects are routinely reported to the contact nurse by telephone, in practice this happens on the same day or within a few days after side effects occur. In connection with the project, participants in the intervention group will receive the same information about side effects as in routine clinical practice, supplemented by corresponding information about the need to report by telephone to the contact nurse in the event of side effects. Furthermore, all participants are asked about side effects at the ½-year and 1-year follow-up visits. In each individual case, an assessment will be made by one of the clinic's specialists (senior physicians) as to whether side effects should lead to dose reduction or discontinuation. All reported side effects are entered into the participant's CRF. As by clinical routine, all participants and relatives will be encouraged to contact the contact nurse by telephone in case of any suspicion of side effects. If the reported side effects are deemed to be related to the medicine, common practice is to either switch to an alternative anti-dementia drug or reduce the dose. It depends on a medical assessment whether there is a basis for changing the preparation or reducing the dose. In all such cases, in connection with the project, a blood test will be offered to determine the serum concentration. Common side effects (in 1-10% of subjects): Less than 5% of patients who have a blood test will develop a minor hematoma at the insertion site [of the needle]. This side effect is benign and will disappear without any treatment. Slight pain at the injection site itself and subsequent mild soreness may occur. It may occur that participants who are uptitrated in dose on the basis of low serum concentrations will develop side effects. These are mainly mild gastrointestinal side effects, and in rare cases cardiac side effects. Occurrence

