of such potential side effects will be closely monitored and the clinic will immediately respond accordingly. Apart from the time consumption of the cognitive tests and interviews, there are no other known side effects of these studies. There are no side effects or significant risks when recording standard EEG with modified photo-block. The participants can at any time during the EEG recording refuse to complete this study, which must then be complied with by the person in charge of the experiment. In this context, an adverse event (AE) is defined as: any adverse event in a patient or subject in a clinical trial after treatment with a medicinal product, without necessarily having a connection between this treatment and the adverse event.

Registration of unwanted events

All of the following information is recorded by the physician in charge of the study for each adverse event:

- Complete description of the unwanted event.
- Date and time of onset.
- Date and time of resolution.
- The severity of the incident must be assessed by the physician responsible for the study [primary investigator] according to the definitions below.
- Whether or not it is a serious incident.
- Whether the incident was expected or not.
- The relationship to the procedure, which must be assessed by the physician responsible for the study according to the definitions below.
- Action taken (if applicable).
- Result and information for all further follow-ups. Definitions of adverse event severity.

The following are the only definitions used to describe the severity of adverse events:

- Mild – The adverse event does not interfere with the subject's daily routine. It causes slight discomfort.
- Moderate – The adverse event interferes with some aspects of the subject's daily routine.
- Severe – The adverse event causes an inability to perform the subject's daily routine. Only one definition of severity is used for each adverse event (eg a statement such as "mild/moderate" is not acceptable). Moderate or serious adverse events are considered very unlikely in the present project.

Serious adverse events

A serious adverse event (SAE) is understood in this context as all medical occurrences, such as:

- results in death,
- is life-threatening,
- requires hospitalization or extension of an existing hospital stay, results in permanent or significant disability, or inability to work.

Adverse events that meet all of the following criteria:

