The study is intended to be conducted as a prospective single-blind randomized controlled study with a follow-up period of one year. This means that the professional who carries out tests and assessment of clinical effect as well as registration of the occurrence of side effects is unaware of whether the patient is in the control or intervention group.

Side effects

Common side effects (in 1-10% of the test subjects): A small proportion of the patients who have their dose increased on the basis of the blood concentration determination will be able to develop side effects, mainly from the gastrointestinal tract in the form of nausea, abdominal pain or loose stools. Mild headache and dizziness may also occur. The side effects are benign and will disappear after dose reduction without any treatment. Uncommon side effects (in 0.1-1% of participants): supposedly less than 1% may have transient cardiac side effects after increasing the dose based on the blood concentration measurement, typically problems associated with bradycardia (dizziness, fatigue, general malaise). These inconveniences are generally of a completely benign nature, and disappear quickly when the dose is reduced. Rare side effects (in 0.01-0.1% of participants) and very rare side effects (in less than 0.01% of participants): Transient liver effects, muscle cramps, heart block and muscle stiffness are seen in rare cases. Likewise, these side effects are generally reversible upon dose reduction.

Ethical considerations

The study will follow the Helsinki declaration of 1984, which was modified at the 41st World Congress in Hong Kong 1989. The study is approved by the Regional Scientific Ethics Committee for Region Zealand and the Data Protection Authority (we assess that the study is covered by Region Zealand's umbrella approval from the Data Protection Authority, and the study has been registered accordingly). Participants will only be included after full written and oral information and written informed consent. The participants can withdraw

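### The planned between-arm comparison of side effects is at risk of unequal capture, and the documents disagree on whether side-effect registration is blinded

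*Combined protocol and SAP*

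**What the plan says.** **The comparison.** The Recruitment section states: "A comparison is made of the occurrence, duration and outcome of side effects in the 2 groups". It adds the proportions who switch preparation or stop because of side effects.

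**How side effects reach the record.** The Side Effects and Adverse Events section says that intervention participants get the routine information, "supplemented by corresponding information about the need to report by telephone to the contact nurse in the event of side effects". The same section says that "all participants and relatives will be encouraged to contact the contact nurse by telephone in case of any suspicion of side effects" and that "all participants are asked about side effects at the ½-year and 1-year follow-up visits". Every reported side effect goes into the CRF.

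**What a report leads to.** Under Inclusion interview/recruitment: "Participants in the intervention group are offered an extra blood test if side effects develop within 2 weeks to 2 months after starting treatment". For controls: "Participants belonging to the control group will not undergo any extra procedures, apart from a single blood test at the end of the project". The same list has the project nurse tell participant and relative their allocation.

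**Who registers, and blind or not.** The lay summary (Design) says that the professional who does the testing and rates clinical effect "as well as registration of the occurrence of side effects is unaware of whether the patient is in the control or intervention group". Registration of unwanted events says: "All of the following information is recorded by the physician in charge of the study for each adverse event". That physician also grades severity and judges relationship. Inclusion interview/recruitment gives decisions on dose adjustment to the person in charge, not to the project manager. Both places gloss the role as primary investigator. Study design limits rater blinding to clinical function, and the Blinding section names only the project manager.

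**The concern.** A fair comparison of side-effect occurrence needs the same chance of recording an event in each arm. Here the participants and relatives who report are unblinded. Reporting early has a practical consequence in the intervention arm, and the text describes extra information about phoning for that arm alone. All three features point towards fuller capture of early events in the intervention arm. If that happens, a real reduction from monitoring could be hidden, or an excess could appear where there is none.

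Blinded registration would protect the recording and grading steps, though not the participant's decision to report. The lay summary claims that protection, but the main text does not clearly provide it. The trial's title and the lay summary's stated purpose both include the effect of monitoring on side effects, so readers will look for this comparison.

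**Working it through.** **1. The plan's own figure.** The only sample-size calculation is in Statistics and power calculation: (1.96 + 0.84)² × (0.5×0.5 + 0.75×0.25) / 0.25² = 7.84 × 0.4375 / 0.0625 = 54.88, so 55 per group and 110 in total. It reproduces. It concerns optimised clinical effect, not side effects, and is used below only for the arm size.

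**2. The texts side by side.**

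| Question | One place | Another place |
|---|---|---|
| Who is told to phone? | Supplementary information, intervention arm (Side Effects and Adverse Events) | Everyone encouraged to phone (same section) |
| Who is offered a blood test after side effects? | Intervention arm, early side effects (Inclusion interview/recruitment) | All cases judged drug-related, no arm named (Side Effects and Adverse Events) |
| Who registers events? | A professional unaware of the arm (lay summary, Design) | The physician in charge (Registration of unwanted events) |
| Who handles dose changes? | The person in charge; kept away from the project manager (Inclusion interview/recruitment; Blinding) | The project manager arranges a reduction if side effects follow an increase (Ethical considerations) |

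In the intervention arm, dose adjustment follows serum values, so whoever decides it will learn the arm. If the same person records and grades events, registration is not blind. This is a strong inference; no sentence states it. Naming the project manager as registrar would not clearly settle the matter, because of the last row.

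**3. Possible size (illustration only).** The documents give no overall side-effect rate on treatment by arm and no probability that an event is recorded. Assume:

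- reported rate = true rate × capture;
- 55 per arm and a two-sided 5% chi-square test without continuity correction;
- rejection probability by exact enumeration of two independent binomials.

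Equal true rates, so any significant result is false:

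| Capture, intervention / control | True rate 10%: reported rates, rejection | True rate 40%: reported rates, rejection |
|---|---|---|
| 90% / 90% | 9% vs 9%, 4.9% | 36% vs 36%, 5.3% |
| 90% / 80% | 9% vs 8%, 5.3% | 36% vs 32%, 7.6% |
| 90% / 70% | 9% vs 7%, 6.4% | 36% vs 28%, 15.0% |

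A true benefit, 25% with monitoring against 40% in controls:

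- Equal 90% capture: 0.25×0.9 = 22.5% vs 0.40×0.9 = 36%. Power 34.5%.
- 90% intervention, 70% control: 22.5% vs 0.40×0.7 = 28%. Power 10.1%. The visible difference shrinks from 13.5 to 5.5 points.

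A benefit can also vanish. True rates of 20% vs 30% with capture of 90% vs 60% give 0.20×0.9 = 18% and 0.30×0.6 = 18%.

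**The case against.** A reader might infer that only the intervention arm is told to phone. The documents do not support that. Phoning the contact nurse is described as existing routine, everyone is encouraged to do it, and everyone is questioned at both visits. In a translated text the supplement may be little more than a change of emphasis. This stands, and it makes a large capture gap harder to assume. With a ten-point gap and a low event rate, the false-positive rate is close to nominal. It does not remove the arm-specific consequence of an early report or the open allocation.

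A reader might also infer that registration is plainly unblinded. That goes beyond the text. The section on unwanted events concerns the safety record. Decisions on reduction or discontinuation for side effects belong to one of the clinic's specialists, and nobody is named as making the CRF entry. The lay summary may mean the questioning at visits by a blinded tester. This partly stands: the passages need reconciling, and the unblinded status of the registrar is an inference from roles.

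Finally, side effects are not in the list of quantitative outcome variables or in the sample-size basis, and the Study hypotheses section does not claim that monitoring reduces them. This limits the weight of the point. The comparison is still planned in so many words.

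Restricting the analysis to visit answers would be a poor remedy. Early side effects are a named aim, duration is to be compared, and patients with dementia may forget brief events. That objection is accepted and shapes the fix.

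**Conclusion.** The point holds as a risk of differential ascertainment. It would be too strong to say that the comparison is biased, because the documents do not show that capture differs or by how much. If capture is equal there is no distortion. Under the stated assumptions (55 per arm, equal true rates of 10% to 40%), the false-positive rate is about 5.3% to 7.6% with 90% versus 80% capture. It reaches 15% with 90% versus 70% at a true rate of 40%. The likely direction, more recorded events in the intervention arm, is a judgement from the design.

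The lay summary's claim of blinded side-effect registration does not fit the main text and should not be relied on as it stands. The point is worth acting on because it changes what the side-effect comparison can conclude, but it does not touch the powered comparison.

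**What to change.** 1. Make the main between-arm comparison the side effects elicited by the same question in both arms at the half-year and 1-year visits.
2. Report all CRF-recorded side effects, phoned-in events included, as a supporting analysis split by source (phone or visit) and by arm, and interpret it as open-label.
3. Keep the planned comparison of switching or stopping, noting that those decisions are also unblinded.
4. Reconcile the two reporting sentences in Side Effects and Adverse Events, and reconcile that section with Inclusion interview/recruitment on who is offered a blood test.
5. Reconcile the lay summary with Registration of unwanted events, Inclusion interview/recruitment, Study design and Blinding. Claim blinding only for the rating of clinical function unless a blinded registrar of side effects is identified.

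The cost is mainly analysis and reporting text. Recruitment ended in February 2022, so the information given at enrolment cannot be changed. Item 2 assumes that the source of each report can be recovered from the CRF or medical record. The downside of item 1 is that brief early events may be under-recalled at the half-year visit, possibly not equally: an event that led to a call and a blood test may be remembered better. Item 2 is kept alongside for that reason. Visit answers still come from people who know their arm, so the change reduces the asymmetry without removing it.

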Electroencephalography Electroencephalography (EEG) is a method in which electrodes are placed on the head and the electrical activity of the brain is measured. After recording, these measurements can be exported and cleaned up using different software, after which separate calculations can be made on the basis of the signals. In this case, we will calculate the connection between the signals using coherence. During the EEG recording, you will be stimulated with stroboscopic light for a few minutes (during the so-called 'photo-block'). In relation to clinical standard EEG, the photo-block is modified with regard to optimal study of quantitative EEG measures of relevance to the project. The photo block is composed as follows: 30 seconds with 1 Hz stimulation, 30 seconds break with eyes open. Then respectively 8-10-12-14 Hz stimulation for 10 sec. separated by short breaks of the same duration. After this 40 Hz stimulation for 10 sec. followed by a one-minute break. The photo-stimulation ends with 30-second stimulation of three rounds of 35, 45 and 55 Hz. each separated by a one-minute break.

Study hypotheses

- The clinical effect of anti-dementia drugs can be increased significantly through plasma concentration determinations and dose adjustment based on this.
 - In clinical practice, patients treated with anti-dementia drugs generally do not achieve the recommended plasma concentration
 - Patients treated with anti-dementia drugs who experience early side effects are often patients who, on low or standard dosages, have plasma concentrations above the recommended level.
 - The cause of plasma concentration above or below the recommended level is often aberrant metabolism due to genetic variation

[figure not shown]
- There is a gender difference in relation to plasma concentration at recommended dosage
- Treatment compliance can be improved significantly through plasma concentration determinations in the event of side effects and in the case of unsatisfactory clinical effect of anti-dementia drugs
- EEG coherence in the alpha band will be higher after starting treatment with Donepezil

Possible impacts of the project

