- Approx. 30 patients will have a standard EEG with modified photo-block performed, if Donepezil treatment has not been started beforehand. These approx. 30 patients will have another standard EEG performed with the same modified photo-block approx. one year later in connection with the point below.
- After one year, all participants are called for one additional visit. Here, a blood test is carried out on all participants, just as all participants are offered a dosage adjustment depending on the serum concentration, also if appropriate a change of preparation. The same clinical tests are carried out as during the preliminary examination [or enrollment visit]. All participants are asked about treatment compliance.

- If there is a need for dose adjustment or possibly prescription change during the project, the decision will be made by the person in charge of the experiment [primary investigator] and not the project manager (PhD student). Practical handling is carried out in collaboration between the project manager and the project nurse.
- A blinded calculation of the distribution of serum concentration, clinical scores, compliance and occurrence of side effects [is done by a statistician not affiliated with the study]

Study visits

- In connection with the information interview, as part of the general clinical course, the initial information about the project is provided and project information is provided.
- Potential participants are contacted to participate in one extra visit (inclusion interview with project manager) together with the relative.
- If informed consent is obtained, one extra visit to the clinic 1 year after enrollment ["1 year follow-up visit"]. The visit ½ year after enrollment is part of the routine follow-up at RVD.

End of study

The study is ended on the date when the last participant (cf. power calculation) has been evaluated at the 1-year follow-up visit. Subsequently, after registration and [external] monitoring [of data quality], data will be transferred to blinded statistical analysis by a statistician. A need for future follow-up visits will be conducted at the GPs office.

Study design

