Based on clinical database information, 15-20 newly referred patients eligible for study participation will likely be referred to RVD per month. If it is assumed that approx. half will participate in the project, approx. 100 patients could be included in one year.

If it is assumed that <50% of the participants reach the recommended serum concentration and thus relevant clinical effect on standard dosing (cf. pilot study), and that this can be increased to 75% by dose adjustment after S concentration determination, the following calculation can be performed on the basis of the formula:

$$N > (Z_{2\alpha} + Z_{\beta})^2 \times (P_1(1-P_1) + P_2(1-P_2)) / (P_1 - P_2)^2$$

where N is the number of necessary participants in each group, α is significance level 5%, β is the probability of type 2 error (strength is $1-\beta = 80\%$), P_1 is dose optimization (optimized clinical effect) with regular dosing, P_2 is dose optimization (optimized clinical effect) guided by S-level and possibly side effects.

$$N > (1.96+0.84)^2 \times (0.5 \times 0.5 + 0.75 \times 0.25) / 0.25^2 = 7.84 \times (0.25 + 0.1875) / 0.0625 \sim 55$$

In other words, 110 participants must be included in the project period in order to calculate the clinical utility of serum concentration measurements with the stated assumptions. Realistically this goal for participant recruitment can be reached within a study period of one to two years.

Risk assessment (risks and discomfort)

Blood test

For all participants in the study a single blood sample is collected for genetic analyses. For the intervention group, as stated, a single blood sample is also taken in case of side effects, and after $\frac{1}{2}$ and 1 year. The blood sample is collected in a completely routine manner by a trained professional. The procedure is not associated with any other discomfort or inconvenience, apart from what is known for a routine blood test in a normal clinical context. For the control group, a blood sample is collected at the 1 year follow-up visit, when the CRF is closed for that participant.

MMSE, ACE, GDS, DAD, NPI

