- Unexpected (i.e. inconsistent with common knowledge about potential side effects)
- There is at least a reasonable possibility that there is a causal connection between the incident and the procedure will be classified as Suspected Unexpected Serious Adverse Reactions (SUSAR).

The assessment of the relationship between an adverse event and the procedure (probable, possible, unlikely, none, cannot be assessed) is a clinical decision based on all available information. Factors that should be considered in the relationship assessment include the temporal sequence from the time of the procedure, improvement upon cessation (withdrawal) of the procedure, underlying concurrent competing illnesses, concurrent medical procedures or treatment, known pattern of response to methods used, exposure to physical and/or psychological stress. The physician in charge of the study, senior doctor [consultant] [name], is responsible for evaluating whether an adverse event

is serious or not and, in case of doubt, relevant information will be obtained and reported in detail. The product summaries for Donepezil and Memantine are used to assess whether a serious related side effect is expected. All adverse events in connection with the experiment will be registered and reported, cf. legislation, to the authorities. The sponsor is required to ensure that all information about SUSARs, which are fatal or life-threatening, is registered and reported to the Danish Medicines Agency as soon as possible and no later than 7 days after the sponsor has become aware of such a suspected side effect. No later than 8 days after the report, the sponsor must notify the Danish Medicines Agency of all relevant information about the sponsor's and investigator's follow-up to the report. All other SUSARs must be reported to the Danish Medicines Agency no later than 15 days after the sponsor has become aware of them.

Monitoring subjects with adverse events

All adverse events that occur during the study must be monitored and followed until they have either resolved, returned to normal or baseline values, reached clinical stability, or been shown to be unrelated to the project.

Ethical considerations

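### The side-effect comparison does not say whether it counts all recorded events or only attributed ones, and attribution is unblinded with serum results that mostly exist in one arm

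*Combined protocol and SAP*

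**What the plan says.** **The comparison.** Under Recruitment (see FLOWCHART), the protocol compares the two groups on how often side effects occur, how long they last and how they end, "including the proportion of patients who had to change preparations or abandon medical treatment due to side effects". It does not say whether the events compared are all those recorded or only those attributed to the drug.

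**Who records and rates.** Under Registration of unwanted events: "All of the following information is recorded by the physician in charge of the study for each adverse event". The items include the relationship to the procedure, rated by the physician responsible for the study, whom the same list identifies as the primary investigator. Under Serious adverse events, the rating "is a clinical decision based on all available information". Serum concentration is neither named among the factors to consider nor ruled out.

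**Who decides on dose.** For dose or prescription changes, Study execution and visits says "the decision will be made by the person in charge of the experiment [primary investigator] and not the project manager (PhD student". In the intervention group these decisions use the serum result.

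**Who is blinded.** Recruitment, Study design and Blinding cover the project manager or test rater and the statistical analysis. None of them covers the physician in charge.

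**Who has serum results.** The Introduction, Recruitment, Study execution and visits, and the blood-test part of Risk assessment give the intervention group a sample for early side effects and one at half a year, and give controls serum only at 1 year. Two sentences do not fit: a half-year sample described as being for every participant (Study execution and visits), and a sample offered whenever a side effect is judged drug-related, with no arm named (Side Effects and Adverse Events).

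**The concern.** A count of side effects, or of treatment stopped because of them, can rest on a judgement that the drug was the cause. Here the person making that judgement sees the serum level for many intervention participants and, before 1 year, for few or no controls. The trial's own hypothesis is that patients with early side effects often "have plasma concentrations above the recommended level". A rater who holds that view could lean towards a drug cause when the level is high, and away from it when the level is in range or low. The rule reads the same for both arms but is applied to different evidence. This would act even if participants in both arms reported events identically.

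At stake is whether a difference in side effects reflects serum guidance or merely access to serum results. Under Monitoring subjects with adverse events, follow-up may also end once an event is shown to be unrelated, so duration and outcome could be affected too.

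**Working it through.** **1. The plan's only design calculation.** Statistics and power calculation gives (1.96 + 0.84)² × (0.5 × 0.5 + 0.75 × 0.25) / 0.25² = 7.84 × 0.4375 / 0.0625 = 54.88, rounded up to 55 per group. It reproduces. It concerns optimised clinical effect, not side effects, so it supplies only the group size used below. The documents give no side-effect rate by arm and no attribution rate.

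**2. Which comparisons need attribution.**
- *Occurrence:* Side Effects and Adverse Events sends all reported side effects to the CRF, and Recruitment sends all possible side effects or unwanted events there. No causality filter is stated. Occurrence is exposed only if the analysis counts attributed events, which the plan leaves open.
- *Change or abandonment because of side effects:* exposed by definition, since it needs a cause.
- *Duration and outcome:* exposed in so far as follow-up ends on a finding of unrelatedness.

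**3. When serum is known.** Under Side Effects and Adverse Events, an effect is first judged drug-related and the blood test is then offered. Early events are therefore less exposed. Events after the half-year result, and ratings entered after a result has come back, are not protected by this order.

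**4. Possible size.** All inputs except n = 55 are assumptions. Let r be the true proportion with an event, equal in both arms (20% to 50%), and let a_C and a_I be the shares attributed to the drug in the control and intervention arms. Observed proportions are p_C = r·a_C and p_I = r·a_I, with d = p_I − p_C and p̄ their mean. For a two-sided 5% test:

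P(reject) = Φ((|d| − 1.96·se0)/se1) + Φ((−|d| − 1.96·se0)/se1), where se0 = √(2p̄(1 − p̄)/n) and se1 = √((p_C(1 − p_C) + p_I(1 − p_I))/n).

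Example: r = 30%, a_C = 80%, a_I = 70%. Then p_C = 24%, p_I = 21%, |d| = 3 points, se0 = 0.0796, se1 = 0.0796, and P(reject) = 6.6%.

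Spurious gap in percentage points, with P(reject) in brackets:

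| Attributed, control / intervention | r = 20% | r = 30% | r = 40% | r = 50% |
|---|---|---|---|---|
| 80% / 80% | 0 (5.0%) | 0 (5.0%) | 0 (5.0%) | 0 (5.0%) |
| 80% / 70% | 2 (6.0%) | 3 (6.6%) | 4 (7.4%) | 5 (8.4%) |
| 80% / 60% | 4 (9.2%) | 6 (12.0%) | 8 (15.3%) | 10 (19.4%) |
| 80% / 50% | 6 (15.4%) | 9 (22.0%) | 12 (29.8%) | 15 (38.8%) |

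Swapping the shares between arms gives the same sizes with the opposite sign. If all recorded events are counted, attribution drops out and the first row applies.

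**The case against.** The strongest reply is that the causality rating is never tied to the comparison. It sits in the text on serious-event reporting, grades relationship to the procedure, and does not list serum level. All reported side effects go into the CRF, relatedness comes before the blood test for early events, and the lay summary (Design) says that whoever registers side effects is unaware of the arm.

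Much of this stands. A reader might infer that the occurrence comparison is already biased by attribution; the documents do not show that, because no passage filters events by relatedness. But no passage commits to counting all events either, and treatment stopped because of side effects needs a judgement of cause in any case. The rating appears to cover the drugs, since the same section uses their product summaries to judge whether a related serious side effect is expected. The lay summary's claim conflicts with Registration of unwanted events, where the physician in charge records every event.

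A reader might also infer a specific spurious benefit. In the pilot, 18 of 24 samples (8 in range, 10 below) were not above the range. If 20% of such events were re-judged as unrelated, 0.75 × 0.20 = 15% of intervention events would be lost, and an assumed 30% incidence would read 25.5%, a 4.5-point gap. The documents do not support that figure. The pilot samples are not described as coming from patients with side effects, only downgrading is modelled, and events before any serum result are included. It is also only about half the standard error of the difference, √(2 × 0.3 × 0.7/55) = 8.7 points.

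Finally, Side Effects and Adverse Events gives the decision to reduce or stop to one of the clinic's specialists, not only to the physician in charge. That adds a passage to reconcile, but those specialists are not covered by the stated blinding either.

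**Conclusion.** The concern holds as an unspecified analysis combined with an unblinded, arm-dependent judgement. The plan should say which events the side-effect comparison counts, and should not rest its main harm comparison on attribution. The most exposed item is change or abandonment because of side effects; early events are less exposed.

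Bias is a credible risk, not a demonstrated result, and its direction is unknown. Under the assumed ranges the gap runs from 2 points to 15 points either way, and it is zero for an all-event count. The conclusion assumes that serum results before 1 year are confined to the intervention arm. That is the better-supported reading, but the two conflicting sentences need to be settled.

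**What to change.** State in the SAP, before the data go to the statistician:

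1. The main between-arm harm comparison is the proportion of all randomised participants with at least one adverse event recorded in the CRF, whatever its attributed cause.
2. Attributed side effects, and change or abandonment because of side effects, are secondary and labelled as unblinded judgements.
3. A sensitivity analysis re-grades relatedness from a CRF listing with arm, serum values and mentions of extra sampling removed. Existing staff whose blinding is confirmed should do this. The project manager cannot be assumed to qualify: Ethical considerations has that role arrange dose reductions and act on the serum value, while Blinding keeps dose adjustment away from it.
4. Drug change for any reason is not used as a harm endpoint, because serum-guided switching is part of the intervention and would raise that count by design.
5. The protocol passages on who is sampled, who records side effects, who decides on changes and who is blinded are reconciled: Study execution and visits, Side Effects and Adverse Events, Registration of unwanted events, Blinding, Ethical considerations, and the lay summary.

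The cost is SAP wording, one masked listing and some staff time. The data are already collected, which matters because recruitment ended in February 2022 and the last visit was expected in March 2023. Asking for relatedness before serum is opened could not cover earlier events. The downside is that all-event counts include unrelated events and slightly dilute a true drug-related difference. They also do not correct any difference in reporting, and Side Effects and Adverse Events describes supplementary reporting information for the intervention group.
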